3.1.7.3 Intercurrent Event Caused by COVID-19

The Statistical Considerations for Clinical Trials During the COVID-19 Public Health Emergency Guidance for Industry states the following: “For a trial with sites closed for a period of time because of COVID-19, the missing endpoint ascertainment during this period may not necessarily be related to the treatment assignment or participant characteristics and outcomes. In this case, removing all participants from closed sites who were scheduled for an endpoint ascertainment from the analysis should not bias the findings.... if the closure of a site for a certain period of time greatly impacts trial specified treatment for participants such that it is unlikely that any treatment effect can be observed, then it may be reasonable to exclude participants who were impacted during that period of time” (FDA, June 2020).

Following this guidance, if a patient misses 3 consecutive doses or more due to site access restriction caused by the COVID-19 public health emergency, the assessments after the dose interruption will be treated as missing in the analysis. A sensitivity analysis including all data collected will be conducted (see Section 3.2.1).

3.2 Analysis Populations

3.2.1 Intention-to-Treat (ITT) Population

The ITT Population is defined as all enrolled/randomized patients (enrolled for Cohort 1 and 2 and randomized for Cohort 3) who receive at least one dose of study drug. The ITT Population will be the main population for analysis of efficacy endpoints; the analysis will include all assessments from all patients with the exception of the missing assessments due to missing 3 doses, whereas a sensitivity analysis will include all assessments from all patients. The ITT and Safety Populations (see definition in Section 3.2.3) are identical except in the case that any patient in Cohort 3 was not dosed as randomized. The ITT Population is analyzed as randomized.

3.2.2 Per-Protocol (PP) Population

The PP Population is defined as all patients in the ITT Population who completed the study with no major protocol deviations that may impact the primary efficacy assessment. The PP Population will be a secondary population for analysis of the primary efficacy endpoint. Major protocol deviations that may impact the primary efficacy assessment may include but are not limited to:

- Failed to meet eligibility criteria;
- Took the wrong study drug (i.e., did not take the randomized study drug or full dose);
- Had study drug compliance <80%;
- Took a restricted concomitant medication; or
- Failed to complete the efficacy assessment at certain time points.

A list of patients with major protocol deviations leading to exclusion from the PP Population will be finalized prior to the Sponsor's review of the efficacy data and before unblinding of the randomized treatment assignments.

3.2.3 Safety Population

The Safety Population is defined as all enrolled/randomized patients who receive at least one dose of study drug. All safety data will be analyzed using the Safety Population. In the event that a patient takes the wrong study drug (i.e., did not take the randomized study drug), the actual treatment received will be used for analysis. The ITT Population is the same as the Safety Population except in the case that any patient in Cohort 3 was not dosed as randomized. The Safety Population is analyzed as treated.

3.2.4 Pharmacokinetic Population

The PK Population will include all patients who are enrolled/randomized and receive at least 1 dose of study drug and have at least 1 quantifiable concentration of PK sample.

3.2.5 Pharmacodynamics Population

The PD Population will include all patients who are enrolled/randomized and receive at least 1 dose of study drug and have at least 1 quantifiable post-baseline PD measurement.

3.3 Subject Data and Study Conduct

3.3.1 Subject Disposition

The following disposition categories will be presented:

- Patients who were enrolled/randomized,
- Patients who completed the Treatment Period of interest at the analysis, and
- Patients who completed the follow-up period.

For patients who did not complete the Treatment Period of interest at the analysis, a summary will be provided for the primary reason of discontinuation.

3.3.2 Protocol Deviations

Protocol deviations will be identified based on the clinical data as defined in the Protocol Deviation Plan. The Protocol Deviation Plan will define all protocol deviations as either CSR reportable or

non-CSR reportable deviations. Counts and percentages of patients with CSR reportable protocol deviations by deviation category will be summarized within each cohort and by dose within Cohort 3 for the ITT Population for the 12-month analysis.

3.3.3 Analysis Populations

Counts and percentages of patients in each analysis population will be summarized by cohort, dose (for Cohort 3), treated with background SMA therapy (for Cohort 1), and in total based on all enrolled/randomized patients.

3.3.4 Demographic and Baseline Characteristics

The following demographic and baseline characteristics will be summarized:

- Age at Informed Consent (years),
- Age at Diagnosis (years)
- Sex,
- Race,
- Ethnicity,
- SMA History (including SMA type, contractures, and scoliosis),
- Number of Maintenance Doses Received,
- SMN2 Gene Copy Number,
- Height (cm),
- Weight (kg), and
- Body Mass Index (kg/m²)

Demographic and baseline characteristics will be summarized with descriptive statistics or counts and percentages of patients as appropriate by treatment within each cohort and in total for the ITT, Safety (if different from ITT), and PP populations.

3.3.5 Medical History

Medical history will be coded to system organ class and preferred term using the Medical Dictionary for Regulatory Activities (MedDRA) version 23.0 or later. Counts and percentages of patients with medical history by system organ class and preferred term will be summarized by treatment within each cohort and in total for the Safety and PP populations.

Medical history capturing the patient's SMA history as well as current and past relevant medical status (surgeries, allergies, and concomitant medications) will be listed.

3.3.6 Prior/Concomitant Medications

Prior medications are any medications stopped prior to the administration of study drug. Concomitant medications are any non-study medications taken concurrently while on study drug, regardless of when the non-study medications are started or ended.

Prior/concomitant medications will be coded to anatomical therapeutic chemical (ATC) class and preferred term using the WHO Drug Mar 2020 or later.

Counts and percentages of patients taking prior and concomitant medications by ATC class and preferred term will be summarized by treatment within each cohort and in total for Safety and PP populations.

3.3.7 Study Drug Exposure and Compliance

Weeks of exposure = (date of analysis Visit or lost to follow-up - date of first dose + 1)/7. Note that the study drug exposure calculation is intended to describe the length of time a patient was exposed to study drug and therefore does not take study drug interruptions into account.

Compliance will be summarized with descriptive statistics for the study overall based on treatment duration and number of infusions from the eCRFs and also based on treatment duration and number of infusions from the EDC.

$$\text{Compliance} = 100 \times (\text{number of injections}) \div (\text{treatment duration in weeks} / 4).$$

For the 12-month analysis, if a patient completed the 52-week Treatment Period per protocol, they should have 13 infusions (1-infusion every 4 weeks). For patients entering Extension Period A, the dose administered at V15/E1 will not be counted as part of the Treatment Period and will be considered as part of the Extension Period. Percent compliance to the study drug regimen will be summarized by treatment within each cohort for the Safety and PP populations with descriptive statistics and with counts and percentages of patients with compliance in the following categories:

- <80%
- 80-120%
- >120%

The compliance for the Extension Period will be calculated separately from the Treatment Period.

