2.2 Study Design

2.2.1 Overview

Study SRK-015-002 (TOPAZ) is an active treatment study to evaluate the efficacy and safety of SRK-015 in patients age 2 through 21 years old with later-onset (e.g., Type 2 and Type 3) SMA. Patients may receive SRK-015 as monotherapy or in addition to a survival motor neuron (SMN) upregulator therapy approved for SMA.

This study will be conducted in approximately 20 study sites across the United States and Europe. Approximately 55 male and female patients with later-onset SMA will be enrolled across 3 separate parallel subpopulations subsequently described as cohorts.

- Cohort 1, N=20: Ambulatory Type 3 patients, age 5 through 21 years old, approximately 10 of whom are not receiving an approved SMA treatment, as well as patients already receiving an approved SMA treatment that had been started after the patient turned 5 years old.

- Cohort 2, N=15: Type 2 and nonambulatory Type 3 patients, age 5 through 21 years old, already receiving an approved SMA treatment that had been started after the patient turned 5 years old.
- Cohort 3, N=20: Type 2 patients, age ≥ 2 years old, already receiving an approved SMA treatment that had been started before the patient turned 5 years old.

Patient participation in the study will consist of 3 parts: Screening, Treatment, and Follow-up. Screening motor function outcome measures will be conducted at least 7 days prior to the first dose. All subsequent motor function outcome measures will be conducted within 96 hours prior to dosing. During the 52-week Treatment Period, patients enrolled in Cohorts 1 and 2 will receive high-dose (20 mg/kg) SRK-015 and patients enrolled in Cohort 3 will be randomized (1:1) in a blinded manner to receive either low-dose (2 mg/kg) or high-dose (20 mg/kg) SRK-015.

All treatments will be administered by intravenous (IV) infusion over approximately 2 hours once every 4 weeks. The first dose will be administered on Day 0 and the final dose on Day 336, for a total of 13 doses. During the Treatment Period, patients will be monitored at the study site through approximately 2 hours postdose. If there are no acute reactions following the first 2 doses for a patient, and if the Investigator determines that it would be safe to do so, the infusion duration can be changed to less than 2 hours but no shorter than 1 hour.

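### The SAP compliance formula divides infusions by elapsed time rather than by doses due, so it misstates compliance for patients who stop mid-interval or whose end date is late

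*Combined protocol and SAP*

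**What the plan says.** SAP 3.3.7 gives exposure as "Weeks of exposure = (date of analysis Visit or lost to follow-up - date of first dose + 1)/7" and notes that this "does not take study drug interruptions into account". Compliance is then 100 times the "number of injections" divided by (treatment duration in weeks / 4). Treatment duration is not defined separately from weeks of exposure.

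For a patient who completes 52 weeks, the section expects 13 infusions and states that "the dose administered at V15/E1 will not be counted as part of the Treatment Period". It has no matching rule for a patient who leaves earlier, and the only end dates it names are the analysis visit and loss to follow-up. Compliance is tabulated as <80%, 80-120% and >120% by treatment within cohort, for the Safety and PP populations.

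The schedule is in SAP 2.2.1: "The first dose will be administered on Day 0 and the final dose on Day 336, for a total of 13 doses". SAP 3.2.2 limits the PP population to patients who completed without a major deviation affecting the primary efficacy assessment, and lists "Had study drug compliance <80"% among the deviations that may count.

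**The concern.** The numerator counts doses given at the start of each 4-week interval, while the denominator counts time elapsed. The two agree only when the interval after the last scheduled dose has just run out. A patient who stops sooner is credited with too few expected doses. A patient whose end date is later than the dosing schedule implies is charged with doses that were never due.

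The Safety Population includes early withdrawals, so its compliance table can misfile patients in either direction. The groups are small (20 in Cohort 1, 15 in Cohort 2, 10 per arm in Cohort 3), so one misfiled patient moves a row by 5, 6.7 or 10 percentage points. For completers with a delayed final visit, the 80% cut-off can also be crossed wrongly, and that bears on PP membership.

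**Working it through.** **Inputs**
- Exposure and compliance definitions: SAP 3.3.7. *Assumption:* treatment duration is weeks of exposure.
- Nominal dosing on Days 0, 28, …, 336: SAP 2.2.1.
- Patients who discontinue dosing are followed for 12 weeks (84 days) after the final dose, or longer for an ongoing event: protocol 6.3.4.
- Visit 15 (V15) is not to be skipped however late it is (SAP 2.2.4), and some patients delayed it (SAP 5.2).
- Dropout days are not in the documents. They are assumed below, with the range shown.

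**Formula.** With k infusions and end date on study day D (first dose on Day 0):

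C = 100 × k / {[(D + 1)/7]/4} = 100 × 28k/(D + 1).

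**1. The plan's own case.** At Day 364, expected doses are 365/28 = 13.04, which reproduces the stated 13. Thirteen infusions give 364/365 = 99.7%; 12, 11 and 10 give 92.1%, 84.4% and 76.7%. The formula works for on-time completers.

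**2. Fully dosed, stopping d days after dose k.** D = 28(k − 1) + d, so the denominator is k − 1 + (d + 1)/28 doses. The shortfall is 1 − (d + 1)/28: 0.96 dose at d = 0, zero at d = 27, and on average 1 − 14.5/28 = 0.48 dose. The true value in every cell below is 100%.

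| Days after last dose | 1 dose | 2 doses | 3 doses | 4 doses |
|---|---|---|---|---|
| 0 | 2800% | 193.1% | 147.4% | 131.8% |
| 5 | 466.7% | 164.7% | 135.5% | 124.4% |
| 13 | 200.0% | 133.3% | 120.0% | 114.3% |
| 21 | 127.3% | 112.0% | 107.7% | 105.7% |
| 27 | 100% | 100% | 100% | 100% |
| 84 | 32.9% | 49.6% | 59.6% | 66.3% |

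Five doses with an end on Day 112 give 140/113 = 123.9%. On nominal dosing days, scores above 120% arise on 23, 18, 13, 9 and 4 of the 28 possible days after doses 1 to 5. After dose 6 or later they do not arise; the maximum is 168/141 = 119.1%.

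**3. One missed dose.** Take a patient who misses one of the first four scheduled doses, receives the Day 84 dose, and leaves on Day 89. The formula gives 84/90 = 93.3% against a true 3/4 = 75%, moving the patient from <80% to 80-120%. Stopping 13 days after the last scheduled dose gives 85.7%. Stopping at 27 days gives the true 75%.

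**4. Late end dates.** The last row of the table shows the reversal when the end date is taken 84 days after the last dose. For completers, 11 of 13 infusions is 84.6%. With V15 on Day 385 the formula gives 308/386 = 79.8%. Day 385 is the first day on which this happens, since Day 384 gives 308/385 = 80.0%. At the edge of the 7-day visit window, Day 371, it gives 308/372 = 82.8%, so only a V15 at least 21 days late crosses the cut-off.

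**The case against.** The strongest reply is that the SAP never equates treatment duration with weeks of exposure. Its completer illustration treats each dose as covering the next four weeks; if duration were measured that way for everyone, the formula would be right. That is fair as far as it goes, but the only duration defined is elapsed time, and it sits just above the formula. A programmer would most likely use it, and nothing tells them otherwise.

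Three stronger readings are tempting and are not supported:

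- A reader might infer that early dropouts who took every dose will generally score 124% to 467%, or that the formula is right only at Day 364. Those percentages depend on the assumed day. Days 28 and 112 are dosing days, where the error is largest within an interval. The formula is exact at the end of every interval (Days 27, 55, 83 and so on), and missed doses are hidden only partly and only at some timings.
- A reader might infer that an inflated score keeps a dropout in the PP population. It cannot, because SAP 3.2.2 already requires completion.
- A reader might take a >120% entry as a sign of overdosing. Protocol 10.2.1.3 defines overdose separately, as at least twice 20 mg/kg, and has it recorded in its own right. Disposition tables and listings would also show who left early.

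The word for injections is an editorial slip; the same section says infusions elsewhere.

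**Conclusion.** The point holds as a minor one. On the natural reading of SAP 3.3.7, the stated rule gives wrong values whenever the end date is not at the end of a dosing interval. It overstates by up to about one expected dose for patients who stop mid-interval, and understates when the end date is late. Because no end date is given for withdrawals other than loss to follow-up, the same fully dosed early withdrawal could land in >120% or in <80%.

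The consequences are limited to the descriptive compliance table in the Safety Population and, for late completers near 80%, possible wrongful exclusion from PP. On-time completers are scored correctly, and the main ITT efficacy analysis does not use compliance. The conclusion rests on reading treatment duration as weeks of exposure, on nominal 28-day dosing, and on dropout days that are assumptions. The documents do not say how many patients would be affected.

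**What to change.** Replace the formula in SAP 3.3.7 with: compliance = 100 × infusions received / number of protocol dosing visits due from first dose to the end of treatment participation, capped at 13 for the Treatment Period. Count a visit as due if it was attended or its window has closed.

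State the end date for early withdrawals as the date of discontinuation, not the end of safety follow-up. Change injections to infusions.

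A denominator taken from calendar days alone, floor(D/28) + 1, should be avoided because of the ±7-day dosing window in protocol 6.1. A patient lost on Day 30 before a second dose still in window would score 50%, and one dosed on Days 0 and 21 and lost on Day 25 would score 200%. Counting visits due gives 100% for both. It also gives 75% for the Day 89 example and 84.6% for the Day 385 completer.

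The cost is a few lines of SAP text and a small derivation change using visit dates and infusion records; no new data are needed.

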3.4 Efficacy Assessment

The study is regarded as 3 separate cohorts. In general, efficacy endpoints will be analyzed for each cohort separately. Cohort 1 will be analyzed as total, and by patients who received SRK-015 as monotherapy or in addition to a SMN up-regulator therapy. Cohort 3 will be analyzed as total, and by dose level.

The ITT Population will be the main analysis population for efficacy parameters. Section 3.1.7.3 specifies intercurrent events caused by the COVID-19 public health emergency. Accordingly, a sensitivity analysis will be performed as defined in Section 3.2.1. The efficacy parameters will be evaluated for the PP Population as further sensitivity analyses.

3.4.1 Cohort 1: High Dose

3.4.1.1 Primary Efficacy Endpoint

The primary efficacy endpoint is the change from Baseline at V15 (Day 364) in RHS total score. Summary statistics will be generated along with the 95% CI based on the Student's t-distribution for the change from Baseline.

The cohort will be analyzed as total and by patients who received SRK-015 as monotherapy and in addition to a SMN upregulator therapy.

A waterfall plot of unit changes from baseline in functional scores will be displayed for each post-baseline visit.

3.4.1.2 Secondary Efficacy Endpoints

The following secondary endpoints will be analyzed for Cohort 1:

- Change from Baseline in RHS score at prespecified timepoints
- Proportion of patients achieving various magnitudes of change in RHS score from Baseline to scheduled visits. For example, proportion of patients achieving (at least) 5 points, 4 points, 3 points, 2 points or 1 point increase in RHS score from baseline to V15 (Day 364), V8 (Day 168) and all other scheduled visits.
- Change from Baseline in 6MWT to V15 (Day 364), V8 (Day 168) and all other scheduled visits
- Change from Baseline in 30-Second Sit-to-Stand to V15 (Day 364), V8 (Day 168) and all other scheduled visits
- Change from Baseline in 10-meter Walk/Run (from the RHS) to V15 (Day 364), V8 (Day 168) and all other scheduled visits
- Change from Baseline in timed rise from floor (from the RHS) to V15 (Day 364), V8 (Day 168) and all other scheduled visits.

For continuous variables, descriptive statistics (n, mean, standard deviation, median, minimum, maximum) will be provided. The baseline, post-baseline values and changes from baseline will be included, and a 95% CI will be provided for change from Baseline. Mean change from Baseline over time and the corresponding standard errors will be reported graphically.

For categorical variables, frequency tables will be provided to display the number and percentage of patients in each category at each visit.

3.4.1.3 Tertiary Efficacy Endpoints

The following tertiary endpoints will be analyzed for Cohort 1,

- Change from Baseline in PEDI-CAT; and
- Change from Baseline in PROMIS Fatigue Questionnaire.

For continuous variables, descriptive statistics (n, mean, standard deviation, median, minimum, maximum) will be provided. The baseline, post-baseline values and changes from Baseline will be included.

For categorical variables, frequency tables will be provided to display the number and percentage of patients in each category and change from Baseline at each visit.

For questionnaires with different domains, the summaries for scores and change from Baseline in each domain and in total will be summarized.

3.4.2 Cohort 2: High Dose

3.4.2.1 Primary Efficacy Endpoint

The primary efficacy endpoint is the change from Baseline to Day 364 (V15) in HFMSE total score. Summary statistics will be generated along with the 95% CI based on the Student's t-distribution for the change from Baseline.

3.4.2.2 Secondary Efficacy Endpoints

The following secondary endpoints will be analyzed for Cohort 2,

- HFMSE total score change from Baseline at prespecified timepoints
- Proportion of patients achieving various magnitudes of change in HFMSE score (e.g., at least 5 points, 4 points, 3 points, 2 points, 1 point) from Baseline to V15 (Day 364), V8 (Day 168) and all other scheduled visits
- Change from Baseline in RULM scores to V15 (Day 364), V8 (Day 168) and all other scheduled visits
- Change from Baseline in number of WHO motor development milestones attained to V15 (Day 364), V8 (Day 168) and all other scheduled visits
- Proportion of patients achieving various magnitudes of change in RULM score from Baseline to V15 (Day 364), V8 (Day 168) and all other scheduled visits
- Proportion of patients who attain a new WHO motor development milestone relative to Baseline at V15 (Day 364), V8 (Day 168) and all other scheduled visits.

The same analysis method as the primary efficacy analysis in Cohort 2 will be used for RULM. The same analysis method as the secondary efficacy analysis in Cohort 1 will be used for the rest of the variables.

3.4.2.3 Tertiary Efficacy Analyses

The following tertiary endpoints will be analyzed for Cohort 2:

- Change from Baseline in Time to limitation on ESNHPT or ESB BT;
- Change from Baseline in PEDI-CAT (total score and each domain)
- Change from Baseline in PROMIS Fatigue Questionnaire.

The same analysis method as the tertiary efficacy analysis in Cohort 1 will be used.

3.4.3 Cohort 3: Low Dose and High Dose

3.4.3.1 Primary Efficacy Analyses

The primary efficacy endpoint is the change from Baseline to Day 364 (V15) in HFMSE total score in the high-dose arm. This analysis will also be performed to evaluate the low-dose arm as well as the entire Cohort 3 in total (i.e., high-dose arm and low-dose arm pooled together).

The difference in the change from Baseline in HFMSE total score will also be explored using descriptive statistics and the corresponding 95% CI based on the Student's t-distribution will be reported.

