11.3. Sample Size Rationale

Sample sizes for each cohort were based on practical considerations. Sample sizes of 15 to 20 patients for each cohort will provide 80% power to reject the null hypothesis involving mean changes from Baseline within each treatment group relative to prespecified alternative hypothesis using a paired t-test with two-sided 5% Type 1 error. [Table 8](#) presents the effect sizes within dose groups that can be detected with 80% power and two-sided 5% Type I error as well as the effect sizes that will reject the null hypothesis of no difference according to two-sided $p=0.05$. As illustration, assuming a 2.5-unit standard deviation (SD) for the change from Baseline for HFMSE, a mean 1.7-unit improvement for HFMSE ($n=20$) and a mean 2-unit improvement for HFMSE ($n=15$) can be detected with 80% power while a mean 1.2-unit improvement in HFMSE ($n=20$) and a mean 1.3-unit improvement in HFMSE reaches two-sided $p=0.05$ (rules out a 0 as the two-sided 95% CI for the change from Baseline).

Table 8: Paired T-test: Reject Null Hypothesis No Mean Change from Baseline

	80% Power		Two-sided p=0.05	
Test significance level, α	0.05	0.05	0.05	0.05
Effect size, $e = \Delta_1 - \Delta_2 / s$	0.66	0.778	0.462	0.543
n (after losses)	20	15	20	15

In addition, the total sample size for Cohort 3 (n= 20) provides 80% power to reject the null hypothesis of no mean change from Baseline against the prespecified difference between doses for a clinically meaningful improvement at a two-sided 5% Type I error for a 1:1 randomization (high dose vs. low dose).

Table 9 presents the effect size which could be detected with 80% power and a two-sided 5% Type 1 error as well as the effect sizes required to reject the null hypothesis of no change from Baseline for comparing Cohort 3 low vs. high dose. If the SD of the change from Baseline is 2.5 units for HFMSE, then a mean 2.4-unit difference between low and high dose will reach two-sided p=0.05 (rules out 0 as the lower two-sided 95% CI as the mean difference between dose groups).

Table 9: Unpaired T-test: Reject Null Hypothesis: No Mean Difference from Baseline

	80% Power	Two-sided p=0.05
Two-sided significance level, α	0.05	0.05
Effect size, $e = \Delta_A - \Delta_0 / s$	1.325	0.926
n per group (after losses)	10	10

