2.2.3 Sample Size Determination

Sample sizes for each cohort were based on practical considerations. The following calculations are to illustrate some scenarios of the power yield by the chosen sample size with certain effect size assumptions.

Sample sizes of 15-20 patients for each cohort will provide 80% power to reject the null hypothesis involving mean changes from Baseline within each treatment group relative to prespecified alternative hypothesis using a paired t-test with 2 sided 5% Type I error. [Table 1](#) presents the effect sizes within dose groups that can be detected with 80% power and two-sided 5% Type I error as well as the effect sizes that will reject the null hypothesis of no difference according to two-sided $p=0.05$. As an illustration, assuming a 2.5 unit standard deviation for the change from Baseline for Hammersmith Functional Motor Scale Expanded (HFMSE), a mean 1.7-unit improvement for HFMSE ($n=20$) and a mean 2-unit improvement for HFMSE ($n=15$) can be detected with 80% power while a mean 1.2 unit improvement in HFMSE ($n=20$) and a mean 1.3-unit improvement in HFMSE reaches two-sided $p=0.05$ (rules out a 0 as the two-sided 95% confidence interval [CI] for the change from Baseline).

Table 1: Paired T-test: Reject Null Hypothesis No Mean Change from Baseline

	80% Power		Two-sided $p=0.05$	
Test significance level, α	0.05	0.05	0.05	0.05
Effect size, $e = \Delta_1 - \Delta_2 / s$	0.66	0.778	0.462	0.543
n (after losses)	20	15	20	15

In addition, the total sample size for Cohort 3 ($n=20$) provides 80% power to reject the null hypothesis of no mean change from Baseline against the prespecified difference between doses for a clinically meaningful improvement at a two-sided 5% Type I error for a 1:1 randomization (high dose vs. low dose).

[Table 2](#) presents the effect size which could be detected with 80% power and a two-sided 5% Type I error as well as the effect sizes required to reject the null hypothesis of no change from Baseline for comparing Cohort 3 low vs. high dose. If the standard deviation of the change from Baseline is 2.5 units for HFMSE, then a mean 2.4-unit difference between low and high dose will reach two-sided $p=0.05$ (rules out 0 as the lower two-sided 95% CI as the mean difference between dose groups).

Table 2: Unpaired T-Test: Reject Null Hypothesis: No Mean Difference from Baseline

	80% Power	Two-sided p=0.05
Two-sided significance level, α	0.05	0.05

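### The pooled Cohort 3 HFMSE change (2 and 20 mg/kg together) is planned with no dose term, so its 95% CI would be about 11% to 21% wider than needed at the dose differences printed in the plan

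*Combined protocol and SAP*

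**What the plan says.** SAP 3.4.3.1 defines the Cohort 3 primary endpoint as the "change from Baseline to Day 364 (V15) in HFMSE total score in the high-dose arm". It then adds: "This analysis will also be performed to evaluate the low-dose arm as well as the entire Cohort 3 in total". The total is spelled out as "the entire Cohort 3 in total (i.e., high-dose arm and low-dose arm pooled together"). SAP 3.4 likewise has Cohort 3 analysed in total and by dose level, and protocol 11.2.2 calls for two-sided 95% CIs within cohorts and by dose group. None of these sections gives the total a dose term or a within-arm variance.

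SAP 3.4.3.1 names the Student's t-distribution only for the difference between arms. SAP 3.4.1.1 and 3.4.2.1 give a t-based CI for the mean change in Cohorts 1 and 2, and that is the natural reading for the Cohort 3 total as well. SAP 3.4.3.2 applies the Cohort 3 primary method to RULM.

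On sizing, protocol 11.3 and SAP 2.2.3 give 0.66 SD as detectable with n=20, illustrated as 1.7 HFMSE units at an SD of 2.5. A second table gives 1.325 SD as the dose difference detectable with 10 per arm. Its text says that a 2.4-unit dose difference would reach two-sided p=0.05, again at an SD of 2.5.

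**The concern.** The two arms are randomised groups that receive a tenfold different dose. A one-sample t interval treats all 20 changes as draws from one population, so a fixed gap between the arm means enters the SD as noise. The gap is not merely hypothetical: protocol 4.7 reports greater HFMSE improvement in the high-dose arm at 6 months, although it gives no size.

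The sizing text meets the same issue. The HFMSE is used only in Cohorts 2 and 3, and Cohort 2 has 15 patients, so an HFMSE example with n=20 can only be the whole of Cohort 3. It uses an SD of 2.5, and the between-dose example uses the same 2.5 as a within-arm SD. If the doses differ, the SD of the 20 pooled changes is larger than 2.5.

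At stake is precision. With no formal testing planned (SAP 3.1.5), confidence intervals are the main inferential output, and this one would be wider than the design requires.

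**Working it through.** **Inputs.** Within-arm SD s = 2.5, n = 20 in total, mean change 0.66 SD, dose differences 2.4 units, 0.926 SD and 1.325 SD (protocol 11.3, SAP 2.2.3). Allocation is 1:1 without stratification (SAP 2.2.2), taken first as exactly 10/10.

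**The plan's own figures.** By exact noncentral t at two-sided 5%, n=20 and 0.66 SD give 79.9% power. Ten per arm and 1.325 SD give 80.0%. Both reproduce.

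**SD of the pooled 20.** Let the arms differ by D (in SD units). The between-arm sum of squares adds 20 × D²/4 to a total with 19 df, so

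pooled SD = s × √(1 + (D²/4) × 20/19).

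- D = 2.4/2.5 = 0.96: 2.5 × √(1 + 0.2304 × 1.0526) = 2.5 × 1.115 = 2.79
- D = 1.325: 2.5 × √(1 + 0.4389 × 1.0526) = 2.5 × 1.209 = 3.02

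With 10/10 arms, the true standard error of the overall mean stays at 2.5/√20 = 0.559, because the dose gap does not vary from trial to trial.

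**Half-widths.** One-sample: t(19) × pooled SD/√20, with t(19) = 2.093. This is 2.093 × 2.79/4.472 = 1.31 at D = 0.96 and 2.093 × 3.02/4.472 = 1.41 at D = 1.325. Grouped by dose: t(18) × s/√20 = 2.101 × 0.559 = 1.17 for any D. Averages over simulated trials are slightly lower, because a sample SD is on average a little below the true one.

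**Simulation** (200,000 trials, 10/10, overall mean 0.66 SD). "Power" here means the chance that the 95% CI excludes zero.

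| Dose difference | Pooled SD | Half-width, one-sample | Half-width, grouped | Coverage, one-sample | Power, one-sample | Power, grouped |
|---|---|---|---|---|---|---|
| 0 | 2.50 | 1.15 | 1.16 | 95% | 80% | 80% |
| 0.926 SD | 2.77 | 1.28 | 1.16 | 97% | 73% | 80% |
| 0.96 SD (2.4 units) | 2.79 | 1.29 | 1.16 | 97% | 73% | 80% |
| 1.325 SD (3.31 units) | 3.02 | 1.40 | 1.16 | 98% | 66% | 80% |

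Relative width is 1.29/1.16 = 1.11 and 1.40/1.16 = 1.21.

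**If the split is not fixed.** The documents do not mention blocking. Under simple randomisation at D = 1.325, the one-sample interval covers 95%, because chance imbalance between arms is then real variation in the overall mean. Its half-width is 1.39 against 1.19 for the grouped analysis, and the chance of excluding zero is 64% against 77%.

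**The case against.** The strongest reply is that little depends on this number. The Cohort 3 primary analysis is the high-dose arm alone. The arm-level results and the between-arm CI are reported anyway, and no testing is planned. The error is conservative and cannot create a false positive. In the 1.325 SD scenario with a pooled mean of 0.66 SD, the low dose sits at 0.66 − 0.6625 ≈ 0 and the high dose at about 1.32 SD. The high-dose analysis then has 96% power with n=10, so only the supplementary average loses. All of this stands, and it limits the weight of the point.

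The lack of any stated blocking also stands as an objection to calling the interval over-covering in all circumstances. It does not remove the loss of precision.

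A reader might infer three stronger things that the documents do not support.

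- That the plan states 80% power for the pooled mean. Protocol 11.3 does say that "the total sample size for Cohort 3 (n= 20) provides 80% power to reject the null hypothesis of no mean change from Baseline", but the sentence goes on to the difference between doses and belongs to the two-arm comparison. The paired-test text opens with "Sample sizes of 15-20 patients for each cohort will provide 80% power to reject the null hypothesis involving mean changes from Baseline" but then refers to each treatment group, and its table "presents the effect sizes within dose groups that can be detected with 80% power". The synopsis ties n=20 to Cohort 1. Only the HFMSE n=20 example points to the pooled cohort, and SAP 2.2.3 presents its calculations as illustrations.
- That 1.325 SD is the dose difference the plan expects. It is a detectable difference. The only dose difference given in HFMSE units is 2.4, so both belong in the account.
- That the Cohort 1 total has the same defect. SAP 3.4.1.1 says "The cohort will be analyzed as total and by patients who received SRK-015 as monotherapy and in addition to a SMN upregulator therapy", so a grouping exists. But no difference between the background groups is given, and their split is approximately 10 in one place and at least 10 in another, so it is not fixed. Any figure there would be invented.

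**Conclusion.** The point holds as a matter of precision in a supplementary estimate. With a 10/10 split and a within-arm SD of 2.5, the CI for the Cohort 3 total is about 11% wider than needed at a 2.4-unit dose difference and about 21% wider at 1.325 SD. With no dose difference there is no loss.

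This rests on three assumptions: that 2.5 is the within-arm SD, as the between-dose example uses it; that the total gets a one-sample t interval, which SAP 3.4.3.1 implies but does not state; and that the split is close to 10/10. Without blocking, the interval covers 95%, but it is still wider (1.39 against 1.19 at 1.325 SD).

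The high-dose primary analysis is unaffected, and no conclusion about efficacy would be made falsely positive.

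**What to change.** In SAP 3.4.3.1, compute the Cohort 3 total as the equal-weight mean of the two arm means, with its 95% CI from a model with dose arm as the only factor (pooled within-arm SD, 18 df when all 20 patients contribute). State that RULM, which inherits the method through SAP 3.4.3.2, is handled in the same way.

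In protocol 11.3 and SAP 2.2.3, state that the HFMSE n=20 example (0.66 SD, 1.7 units) describes the whole of Cohort 3 and uses the within-dose SD with this dose-adjusted analysis.

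The cost is a sentence in each place and one degree of freedom: with 10/10 arms and no dose difference, the half-width is 1.158 instead of 1.154. The model assumes similar variances in the two arms. If the arms turn out unequal in size, equal weighting also costs a little: under simple randomisation the grouped half-width averages 1.19, against 1.15 for the one-sample interval when the doses do not differ.
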